6.5. Blinding

The study design includes a Double-Blind Treatment Period with limited access to the randomization code. The etrasimod and placebo tablets and bottles are identical in physical appearance. The treatment each subject receives will not be disclosed to the Investigator, study site staff, subject, Sponsor personnel involved with the conduct of the study (with the exception of the clinical supply staff and designated safety staff), or study vendors. The IWRS will hold treatment codes for study drug.

Site staff including investigators will be blinded to the following laboratory results while subject is on study treatment: WBC count, WBC differential (percentage and absolute number), and TBNK panel (T, B, NK, CD4+ T cell, and CD8+ T cell count [absolute number and percentage]). The monitoring of WBC count, WBC differential, and TBNK panel during the study are described in Section 10.6.7.2. Additionally, post-baseline esophageal histologic outcomes including eosinophil counts and Eosinophilic Esophagitis Histology Scoring System (EoE-HSS) scores will be blinded to site staff until the end of the study.

Treatment assignments in the Double-Blind Treatment Period and Extension Treatment Period should remain blinded for Sponsor, site staff, and subjects until the Week 24 dose selection analysis, unless that knowledge is necessary to determine a subject's emergency medical care. At the time of the 24-week Double-Blind Treatment Period analysis, the sponsor staff will be unblinded to the initial treatment assignments, but subjects, investigators and site staff will remain blinded. During the Extension Treatment Period, subjects, investigators, and site staff will be

aware that active treatment is being provided; however, they will remain blinded to the dose assignments.

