8. REMOVAL OF SUBJECTS FROM THERAPY OR ASSESSMENT

8.1. Discontinuation of Study Treatment

Study medication must be discontinued in the following instances:

- Unacceptable TEAE or TEAE that, in the judgment of the Investigator, is considered to not be in the best interest of the subject to continue study medication, including:
 - Suspected drug induced liver injury as defined by the 2009 FDA Guidance for Industry [49] and described in Section 10.6.7.1
 - Sustained decrease in absolute lymphocyte count ($ALC < 0.2 \times 10^9$ cells/L) with treatment re-initiation or re-challenge after study treatment interruption due to a confirmed $ALC < 200$ cells/ μ L, as described in Section 10.6.7.2
- Intolerance associated with first-dose cardiac effects (Section 10.6.7.4)

Study medication may be discontinued for the following reasons:

- Lack of clinical improvement or therapeutic benefit by Week 32, as determined by the Investigator
- Loss of clinical response after initial treatment response, as determined by the Investigator, at any time during the Extension Treatment Period
- Subject non-compliance

The Medical Monitor should be notified when a subject is discontinued from study treatment.

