
Pregnancy and Postmenopausal Status Testing Serum pregnancy test for β-hCG (Screening or if positive urine pregnancy test; WOCBP only) Urine pregnancy test for β-hCG (Day 1 and monthly post-Day 1; WOCBP only) FSH (Screening; postmenopausal women only)
	

CBC with Differentials Hematocrit Hemoglobin Mean corpuscular hemoglobin Mean corpuscular hemoglobin concentration Mean corpuscular volume Platelet count Red blood cell count WBC^a count WBC differential count (absolute and %): lymphocytes, neutrophils, eosinophils, monocytes, basophils
	

TBNK Panel^a T, B, NK, CD4+ T cell and CD8+ T cell count (absolute number and percentage)
	

Serum Chemistry Albumin Alkaline phosphatase Alanine aminotransferase Aspartate aminotransferase Bicarbonate Blood urea nitrogen Calcium Chloride Creatinine
	
Glucose Potassium Sodium Total bilirubin Total protein

CCI
	

^a WBC count, WBC differential count, and TBNK panel will be assessed by an independent Medical Monitor during treatment (ie, after Day 1) until completion of the Double Blind Treatment Period dose selection analysis at Week 24 or subject discontinues study treatment (whichever occurs first) while the Investigators will assess the results of these lab parameters during Screening, on Day 1, and during the post treatment follow-up (refer to Section 10.6.7.2).

β -hCG, beta-human chorionic gonadotropin; CBC, complete blood count; FSH, follicle-stimulating hormone; HBsAg, hepatitis B surface antigen; anti-HBc, hepatitis B core antibody; HCV, hepatitis C virus; HIV, human immunodeficiency virus; INR, international normalized ratio; TBNK, T, B, NK, CD4+ T cell, and CD8+ T cell count (absolute number and percentage); WBC, white blood cell; WOCBP, woman of child-bearing potential

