10.6.7. Safety Monitoring Guidance

10.6.7.1. Drug-Induced Liver Injury

There is no published consensus on exactly when to stop a drug in the face of laboratory abnormalities and the decision may be affected by the clinical status of the patient and many other factors. The following can be considered a basic guide. When there is no alternative etiology for persistently elevated liver enzymes, discontinuation of study treatment should be considered, consistent with the United States FDA guidance [49], if:

- ALT or AST $> 8 \times$ ULN
- ALT or AST $> 5 \times$ ULN for more than 2 weeks
- ALT or AST $> 3 \times$ ULN **and** (total bilirubin $> 2 \times$ ULN **or** INR > 1.5)
- ALT or AST $> 3 \times$ ULN with the appearance of fatigue, nausea, vomiting, right upper quadrant pain or tenderness, fever, rash, and/or eosinophilia ($> 5\%$)

See [Appendix 12](#) for suggested actions and follow-up assessments in the event of potential DILI. Information on the grading and management of laboratory abnormalities according to assessed severity is provided in [Appendix 8](#) and [Appendix 9](#).

10.6.7.2. Guidance on Management of Lymphocyte, Neutrophil, and White Blood Cell Counts, and Monitoring for Infections

Etrasimod prevents lymphocyte egress from lymphoid tissues, resulting in a reduction in peripheral lymphocyte count and lymphocyte availability for recruitment to sites of inflammation. Site staff including investigators will be blinded to the WBC count, WBC differential (percentage and absolute number), and the TBNK panel cell count while subjects are on study treatment. During this time, WBC count, WBC differential, and the TBNK panel results will be assessed by an independent Medical Monitor (not involved in any other aspects of study conduct or data analysis) and will direct Investigators on specific actions to take. Blinded values may be released to treating physicians and Investigators as deemed medically necessary to monitor the risk of infection and/or aid in diagnostic work-up as clinically indicated, and/or as a tool to assess the effectiveness of therapeutic interventions for an infection.

ALC

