APPENDIX 9: GUIDANCE FOR THE MANAGEMENT OF CLINICAL AND LABORATORY ADVERSE EVENTS

Clinical adverse events (AEs) and abnormal results of laboratory tests and safety assessments considered to be an AE by the Investigator should be graded according to the severity scale of the Common Terminology Criteria for Adverse Events.

Uniform guidance for the management of AEs is provided in [Figure 2](#).

[figure not shown]
Grade 3 and 4 clinically significant laboratory abnormalities should be confirmed by repeat testing within 3 calendar days of receipt of results and before investigational product discontinuation, unless such a delay is not consistent with good medical practice.

A clinically significant Grade 4 laboratory abnormality that is not confirmed by repeat testing should be managed according to the algorithm for the new AE grade.

Investigational product may be continued without dose interruption for a clinically non-significant Grade 4 laboratory abnormality (eg, Grade 4 creatinine kinase after strenuous exercise, or triglyceride elevation that is non-fasting or that can be medically managed) or a clinical event considered unrelated to investigational product.

Any questions regarding adverse event management should be directed to the Medical Monitor.

Figure 2: Algorithm for the Management of Clinical and Safety Assessment-Related Adverse Events

AE, adverse event; ECG, electrocardiogram; IP, investigational product; PFT, pulmonary function test.

^aRepeat lab tests, ECG, or PFT to confirm AE grade. Clinical adverse event(s) may require additional assessment, therapeutic intervention, and/or consultation with relevant expert.

^bLaboratory and/or clinical AEs should be followed until there is stability, improvement or resolution.

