APPENDIX 12: Liver Safety: Suggested Actions and Follow-Up Assessments

Potential Cases of Drug-Induced Liver Injury

Humans exposed to a drug who show no sign of liver injury (as determined by elevations in transaminases) are termed “tolerators,” while those who show transient liver injury but adapt are termed “adaptors.” In some subjects, transaminase elevations are a harbinger of a more serious potential outcome. These subjects fail to adapt and therefore are “susceptible” to progressive and serious liver injury, commonly referred to as DILI. Subjects who experience a transaminase elevation above $3 \times \text{ULN}$ should be monitored more frequently to determine if they are “adaptors” or are “susceptible.”

In the majority of DILI cases, elevations in AST and/or ALT precede T bili elevations ($>2 \times \text{ULN}$) by several days or weeks. The increase in T bili typically occurs while AST/ALT is/are still elevated above $3 \times \text{ULN}$ (ie, AST/ALT and T bili values will be elevated within the same laboratory sample). In rare instances, by the time T bili elevations are detected, AST/ALT values might have decreased. This occurrence is still regarded as a potential DILI. Therefore, abnormal elevations in either AST OR ALT in addition to T bili that meet the criteria outlined below are considered potential DILI (assessed per Hy’s law criteria) cases and should always be considered important medical events, even before all other possible causes of liver injury have been excluded.

The threshold of laboratory abnormalities for a potential DILI case depends on the subject’s individual baseline values and underlying conditions. Subjects who present with the following laboratory abnormalities should be evaluated further as potential DILI (Hy’s law) cases to definitively determine the etiology of the abnormal laboratory values:

- Subjects with AST/ALT and T bili baseline values within the normal range who subsequently present with AST OR ALT values $\geq 3 \times \text{ULN}$ AND a T bili value $\geq 2 \times \text{ULN}$ with no evidence of hemolysis and an alkaline phosphatase value $< 2 \times \text{ULN}$ or not available.
- For subjects with baseline AST **OR** ALT **OR** T bili values above the ULN, the following threshold values are used in the definition mentioned above, as needed, depending on which values are above the ULN at baseline:

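### Suspected liver injury: Section 8.1 makes stopping mandatory where Section 10.6.7.1 only asks that it be considered, and isolated blinded eosinophilia has no stated route to the site

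*Protocol*

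**What the plan says.** **Stopping.** Protocol Section 8.1 opens its first list with "Study medication must be discontinued in the following instances". Under that list's first bullet, which also mentions the Investigator's judgment, stands "Suspected drug induced liver injury as defined by the 2009 FDA Guidance for Industry [49] and described in Section 10.6.7.1". A second, separate list gives reasons for which medication may be stopped.

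Section 10.6.7.1 describes its own list as a basic guide. Where enzymes are persistently raised and no other cause is found, "discontinuation of study treatment should be considered, consistent with the United States FDA guidance", if any one of four criteria is met:

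1. ALT or AST > 8 × ULN
2. ALT or AST > 5 × ULN for more than 2 weeks
3. ALT or AST > 3 × ULN and either total bilirubin > 2 × ULN or INR > 1.5
4. ALT or AST > 3 × ULN "with the appearance of fatigue, nausea, vomiting, right upper quadrant pain or tenderness, fever, rash, and/or eosinophilia" (> 5%)

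**Blinding.** Section 6.5 states: "Site staff including investigators will be blinded to the following laboratory results while subject is on study treatment: WBC count, WBC differential". Table 3 in Section 10.6.4 defines that item as "WBC differential count (absolute and %): lymphocytes, neutrophils, eosinophils, monocytes, basophils". Under Section 10.6.7.2 an independent Medical Monitor reviews these results and directs Investigators, and blinded values may be released to help a diagnostic work-up. The stated notification triggers are ALC < 0.2, ANC < 1.0 and WBC > 20 (all × 10⁹ cells/L).

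**Related text.** Appendix 9 says that clinically significant Grade 3 and 4 laboratory abnormalities "should be confirmed by repeat testing within 3 calendar days of receipt of results and before investigational product discontinuation", with an exception where the delay would not be good medical practice. Appendix 12 says that potential liver injury cases "should always be considered important medical events, even before all other possible causes of liver injury have been excluded".

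**The concern.** Section 8.1 takes its criteria from a section that gives them a weaker force. An Investigator who starts from 8.1 finds an obligation; one who starts from 10.6.7.1 finds a decision to weigh, with two preconditions.

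Separately, one route into the fourth criterion depends on a laboratory value that the person deciding on dosing does not see. If nobody is told to put the eosinophil percentage and the transaminases together, a subject can meet one of the protocol's own criteria without the site knowing.

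Liver injury is an adverse event of special interest (Section 10.6.8.1.4). Selecting a dose on efficacy and safety is a primary objective (Section 2). SAP Section 18.2.3 tabulates adverse events that lead to stopping treatment. A rule that can be applied in two ways makes that table harder to read.

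**Working it through.** No arithmetic is involved beyond checking values against thresholds, so the passages are set side by side.

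**1. Does the reference to Investigator judgment in 8.1 remove the conflict?** The low-lymphocyte item in 8.1 sits under the same bullet, so it serves as a comparison.

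| Item under the same 8.1 bullet | Force in 8.1 | Force in the detailed section |
|---|---|---|
| Sustained ALC < 0.2 × 10⁹ cells/L | mandatory | mandatory (10.6.7.2) |
| Suspected liver injury | mandatory | to be considered (10.6.7.1) |

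For lymphocytes the two sections agree. For the liver they do not, so the shared bullet does not explain the difference.

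**2. A result that shows the conflict.** Take ALT 9 × ULN with a normal baseline, confirmed on repeat, persistent, and with no other cause found. Since 9 > 8, criterion 1 is met and both preconditions of 10.6.7.1 hold. Section 8.1 then says stop; 10.6.7.1 says consider stopping.

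**3. Logic of the fourth criterion.** The list is joined by and/or, so it reads:

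(ALT or AST > 3 × ULN) AND (fatigue OR nausea OR vomiting OR right upper quadrant pain or tenderness OR fever OR rash OR eosinophilia > 5%)

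Any one of seven features is enough, and six are clinical. The blind matters only if eosinophilia is the sole feature and criteria 1 to 3 are not met.

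**4. A result that shows the gap.** Take persistent ALT 3.5 × ULN with a normal baseline, no other cause, normal bilirubin and INR, no symptoms, and eosinophils 8%.

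- Criterion 1: 3.5 > 8 is false.
- Criterion 2: 3.5 > 5 is false.
- Criterion 3: bilirubin and INR are normal, so false.
- Criterion 4: 3.5 > 3 is true and 8 > 5 is true, so it is met through eosinophilia alone.
- Table 11 places > 3 to 5 × ULN in Grade 2, so the Appendix 9 confirmation step is not engaged.

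The site sees the ALT, and Appendix 12 calls for more frequent monitoring above 3 × ULN. The site does not see the 8%. The monitor sees it, but an eosinophil percentage is not among the three listed triggers, and no text asks the monitor to read the differential against ALT or AST.

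**5. Period of the monitor's review.** The Table 3 footnote ends it when the Week 24 dose-selection analysis is complete or the subject stops treatment, whichever is first. It gives Investigators these results only at Screening, on Day 1 and after treatment. Sections 6.5 and 10.6.7.2 keep sites blinded for as long as the subject is on treatment, which can be to Week 52. On the footnote's wording, nobody is assigned the differential for a subject still on extension treatment after that analysis.

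**The case against.** The strongest reply on stopping is that 8.1 already defers to the Investigator and speaks of suspected injury, so 10.6.7.1 is simply the guidance for reaching that suspicion. That is a possible reading, but the text does not say so, and the lymphocyte item shows that the same bullet carries an unqualified obligation elsewhere.

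On blinding, the reply is that the monitor sees every differential and directs Investigators, that release is allowed, and that the three triggers are not said to be exhaustive. All of that stands. It narrows the gap without closing it, because a permission to release is not an instruction to look.

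Several stronger readings are tempting, and the documents do not support them:

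- **That the fourth criterion requires eosinophilia, so the blind disables it.** It is one alternative of seven.
- **That Appendix 9 is a third, contradictory stopping rule.** It covers only clinically significant Grade 3 and 4 results (ALT or AST above 5 × ULN from a normal baseline), has an exception, and fits the persistence condition in 10.6.7.1. Tension remains only with an unqualified reading of 8.1.
- **That the ≥ 3 × and ≥ 2 × ULN thresholds in Appendix 12 compete with those in 10.6.7.1.** Appendix 12 selects cases for evaluation, and evaluation and stopping thresholds may differ.
- **That qualifying subjects will stay on drug because of the blind.** Meeting the criterion leads, under 10.6.7.1, only to consideration, and raised ALT already prompts closer monitoring.
- **That the dose comparison will be biased.** Treatment is double-blind. Differing site practice would mainly add noise, and the documents show neither its size nor a direction.

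Figure 2 of Appendix 9 and any text after the visible part of Appendix 12 were not available for this check, so nothing here rests on what they might omit.

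**Conclusion.** The concern holds in two limited parts. First, 8.1 and 10.6.7.1 give different force to the same liver criteria; this is plain from the text and needs no assumption. Second, when eosinophilia is the only accompanying feature, the protocol states no route by which the blinded value reaches whoever applies the fourth criterion, and the period of the monitor's review is worded inconsistently. This part assumes that the listed triggers are the ones the monitor would act on.

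The size of the second part cannot be estimated: the documents give no rate of transaminase elevation or of blood eosinophilia. Because of that, and because Appendix 12 already calls for closer monitoring above 3 × ULN, this is a safety-relevant clarification that should be made, but it does not rank as a must-fix. Which stopping rule is right is a clinical question on which this review takes no position.

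**What to change.** - Reconcile Sections 8.1 and 10.6.7.1 so that they carry the same force and the same preconditions. The sponsor decides the clinical content.
- State how the Appendix 9 confirmation step and the Appendix 12 evaluation thresholds relate to that rule, including whether confirmation and the search for other causes come before or after the dosing decision.
- State the information route: when ALT or AST exceeds the level already in the fourth criterion, the existing independent Medical Monitor checks the eosinophil percentage and tells the Investigator whether the protocol's own eosinophilia criterion is met.
- Align the period of the monitor's review between the Table 3 footnote and Sections 6.5 and 10.6.7.2.

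The cost is amended wording and one laboratory alert to a monitor already in place, with no new test or staff. The downside is small: a notification reveals one differential finding for that subject.

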10.6.7.3. Guidance on Monitoring Subjects for Infections

Low lymphocyte counts with the use of other S1P receptor modulators in patients with multiple sclerosis have been associated with serious and atypical infections [43,44]. To date, there have been no reports of PML with the use of etrasimod in clinical studies. Nevertheless, Investigators should remain vigilant in monitoring for signs and symptoms of serious and atypical infections

during the study and after discontinuation of study treatment (ie, the 28-day posttreatment period).

If a subject exhibits signs and symptoms suspicious for PML, study drug must be interrupted and cannot be restarted until diagnostic evaluation is completed and PML has been excluded. The Medical Monitor should be informed of any suspected cases of PML. Refer to [Appendix 10](#) for PML signs and symptoms and case evaluation algorithm. In the evaluation and management of treatment-emergent infections, Investigator may consult with infectious disease or relevant experts, as needed.

All radiologic images (eg, magnetic resonance imaging, computer tomography, X-rays) and diagnostic laboratory test results performed by local laboratories/facilities should be retained as source documents by study sites and made available upon request by the Sponsor for central adjudication as needed. All infections that develop during the study will be reported as AEs on the respective eCRF pages.

10.6.7.4. Guidance for Cardiac Monitoring Following Treatment Initiation or Re-Initiation

Cardiac monitoring following treatment initiation applies to the first dose administered in the Double-Blind Treatment Period (Day 1) and in the Extension Treatment Period (Week 24). The lowest predose HR measurement (by vital signs) will be used for comparison to the postdose measurement (by vital signs). Subjects should receive the first dose of study treatment before 12:00 PM (noon).

First-Dose Heart Rate Monitoring

Cardiac monitoring of at least 4 hours following the first dose (Day 1 and Week 24) will include the following ([Table 4](#)):

- Full baseline vital signs (HR, BP, body temperature, and respiratory rate) and 12-lead ECG will be assessed predose (ie, Baseline)
- After the first dose of study treatment (Day 1 and Week 24), subjects must remain under direct observation at the study site for at least 4 hours.
- At Hours 1, 2, and 3 (\pm 15 minutes) postdose, the HR and BP will be assessed with the subject in the seated position, with the time recorded. If the subject has an HR < 50 bpm evaluate cardiac rhythm by 12-lead ECG to identify any clinically relevant ECG changes.
- At the Hour 4 (\pm 15 minutes) discharge assessment, HR and BP will be assessed with the subject in the seated position and a 12-lead ECG in the supine position will also be performed. Subjects may be discharged from the study site after the Hour 4 assessment if they meet the discharge criteria described in [Table 5](#). Subjects not meeting the discharge criteria will require extended monitoring as described below.
- Subjects experiencing a treatment-related symptomatic event (eg, chest pain, dizziness, palpitations, lightheadedness, shortness of breath, or syncope) associated with reduction of the HR together with clinically relevant 12-lead ECG changes at any time during the 4-hour monitoring period should be discontinued from study treatment.

Table 4: Procedures to Be Performed During the Cardiac Monitoring Period

Procedure	Predose	Hours 1, 2, and 3 Postdose^a	Hour 4 Postdose^a
Blood pressure and heart rate ^b	X	X	X
12-lead ECG	X		X
Assess discharge criteria			X

^a Measurements may be taken \pm 15 minutes of the scheduled time.

^b Heart rate is based on vital signs.

ECG, electrocardiogram

Table 5: Discharge Criteria After Cardiac Monitoring

Subjects will be released from the study site after dosing on Day 1 or Week 24 (but no sooner than 4 hours postdose) when they fulfill all of the following discharge criteria:

• Heart rate \geq 50 bpm or no more than 10 bpm lower than the predose value

• Heart rate is not the lowest value measured during the observation period

• No evidence of second-degree AV block or higher

• No cardiac symptoms (eg, chest pain, dizziness, palpitations, lightheadedness, shortness of breath, or syncope)^a

^a Subjects experiencing a symptomatic event (eg, chest pain, dizziness, palpitations, lightheadedness, shortness of breath, and/or syncope) at any time during the 4-hour monitoring period that is not associated with either a reduction in HR or clinically relevant change in 12-lead ECG, may be discharged provided they meet the other discharge criteria, and deemed appropriate by the Investigator.

Note: Subjects should have written instructions on when to return to the study site and a 24-hour contact phone number to call in the event of any new or worsened cardiovascular symptoms.

AV, atrioventricular; bpm, beats per minute; ECG, electrocardiogram; HR, heart rate

Extended Cardiac Monitoring

Subjects who do not meet discharge criteria at 4 hours postdose will require extended cardiac monitoring:

- Vital signs (BP and HR) will be assessed hourly and a 12-lead ECG may be performed, as clinically indicated, until the subject meets the discharge criteria (Table 5)
- The Medical Monitor should be contacted if the subject does not meet the discharge criteria after \geq 4 hours of extended cardiac monitoring

If an ECG shows a new onset QTcF interval above 500 ms (CTCAE Grade 3), a repeat ECG is warranted, and, if this abnormal finding is confirmed and is considered related to study treatment, then study treatment must be interrupted. Effective diagnostic and therapeutic strategies should be employed.

Reversible causes of prolonged QTcF interval (eg, electrolyte abnormalities like hypokalemia and hypomagnesemia), should be corrected as clinically indicated. When evaluating a subject with new onset QTcF interval above 500 ms, referral to a physician experienced in treating cardiac conduction disorders should be considered. If treatment is interrupted, re-initiation of study treatment can only be considered if the QTcF interval is $<$ 450 ms (males) or $<$ 470 ms (females), the prolonged QTcF interval is not considered related to study treatment, the individual risk benefit is favorable (as determined by the Investigator, in agreement with the cardiologist), and after discussion with the Medical Monitor. If, after re-initiation, the QTcF interval is again prolonged above 500 ms, then study drug must be discontinued.

Cardiac Monitoring Upon Treatment Re-Initiation Following Dose Interruption

The procedure for first-dose cardiac monitoring as outlined above should be performed any time a subject misses study treatment for:

- ≥ 2 consecutive days within the first week of treatment during the Double-Blind Treatment Period or during Week 24 of the Extension Treatment Period or
- ≥ 7 consecutive days after the first week of treatment during the Double-Blind Treatment Period or after Week 24 of the Extension Treatment Period.

Subjects are not to re-initiate therapy until they return to the study site for dosing with cardiac monitoring.

